1.2. Participants

Patients with defined MS (13) were recruited from the MS Centers of Hospitals in the Czech Republic in accordance with the following inclusion criteria: prevailed spastic paraparesis, stable clinical status and treatment in the preceding 3 months determined by neurologist, Expanded Disability Status Scale score (EDSS) ≤ 7.5 (14). The study was powered in order to provide 80% power for weak to moderate effect size (Cohen's $d=0.2-0.5$). 120 people were initially assessed for eligibility, 92 were allocated into three groups; from these 71 participants finished their therapeutic programs. Data of ten patients were discarded upon the visual control, due to the low quality of DTI acquisition resulting in 61 participants entering the central analysis. This sample provides 80% power to detect at $p<0.05$ effects of minimal size $d=0.36$ (weak to moderate effect size). For distribution of participants into groups during the study see Figure 1, for their baseline characteristics see Table 1. All subjects signed an informed

consent form approved by the Ethics Committee of Kralovske Vinohrady University Hospital in Prague (full trial protocol EK-VP/22/0/2014 is available there).

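### Section 1.2 states 80% power for d = 0.2–0.5, but no sample size in the document delivers the lower end; at d = 0.2 power is about one third with the 61 analysed

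*Combined protocol and SAP*

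**What the plan says.** Section 1.2 makes two power statements.

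- **Design statement.** "The study was powered in order to provide 80% power for weak to moderate effect size", with Cohen's d = 0.2–0.5 in brackets. No single design effect, planned sample size, test or sidedness is given.
- **Achieved statement.** For the 61 analysed, 80% power at the 0.05 level for "effects of minimal size $d=0.36$ (weak to moderate effect size").

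The participant counts are in the same paragraph: "120 people were initially assessed for eligibility", "92 were allocated into three groups", "from these 71 participants finished their therapeutic programs", and "Data of ten patients were discarded upon the visual control", "resulting in 61 participants entering the central analysis".

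Section 1.6 names a Wilcoxon test for change between visits and a Kruskal-Wallis test for differences between groups. It adds that the sample was sized for the global effect, not for the 48 regional tests.

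**The concern.** Read plainly, the design statement promises 80% power across a range that starts at d = 0.2. The achieved statement puts the 80% limit at 0.36, so about half of the range lies below it: (0.36 − 0.20)/(0.50 − 0.20) = 53%. Because both carry the same verbal label, the achieved figure looks as if it fulfils the design claim. The reader is not told what power remains at the weak end.

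The power statement supports the global FA comparison, which section 1.5 treats as primary and for which section 1.6 says the sample was sized. If it is taken at face value, a non-significant global change could be given more weight against weak effects than 61 participants can bear.

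**Working it through.** **Inputs.** From section 1.2: power 80%, alpha 0.05, d = 0.2–0.5, d = 0.36, and counts 120, 92, 71 and 61. From section 1.6: a Wilcoxon test between visits. **Assumptions:** two-sided test, all three groups pooled, d equal to mean change divided by the SD of change, and normally distributed changes. The document states none of these, but together they reproduce its own figure.

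**1. Reproduce d = 0.36.** Normal approximation: d = (1.960 + 0.842)/√61 = 2.802/7.810 = 0.359. Noncentral t gives 0.365. Power at d = 0.36 with n = 61 is 80.3% (normal), 79.0% (t) and 77.1% (Wilcoxon, simulated). Other readings do not fit: one-sided gives 0.32, and a comparison of two groups of about 20 gives about 0.88.

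**2. Sample size for the stated range.** Normal approximation: n = (2.802/d)².

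- d = 0.2: (2.802/0.2)² = 196.3, so 197; paired t 199; Wilcoxon about 208.
- d = 0.5: (2.802/0.5)² = 31.4, so 32; paired t 34; Wilcoxon about 35.

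**3. Power at d = 0.2.** Normal approximation: Φ(0.2√n − 1.960). For n = 61 this is Φ(1.562 − 1.960) = Φ(−0.398) = 34.5%. For n = 92 it is Φ(1.918 − 1.960) = Φ(−0.042) = 48.3%. The t and Wilcoxon columns below use the noncentral t, with n multiplied by 3/π for the Wilcoxon.

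| n | Source | Paired t, two-sided | Wilcoxon, two-sided | Paired t, one-sided | Detectable d at 80% (t, two-sided) |
|---|---|---|---|---|---|
| 61 | analysed | 33.6% | 32.3% | 46.0% | 0.365 |
| 71 | finished | 38.3% | 36.8% | 51.0% | 0.337 |
| 92 | allocated | 47.5% | 45.8% | 60.2% | 0.295 |
| 120 | assessed | 58.4% | 56.5% | 70.3% | 0.258 |

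Simulated Wilcoxon power agrees: 32.4% at n = 61 and 46.2% at n = 92. At d = 0.5 every row exceeds 80% (97% at n = 61, paired t).

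**4. Check from the document's figures alone.** Required n varies as 1/d². If 61 participants give 80% power at 0.36, then d = 0.2 on the same scale and test needs about 61 × (0.36/0.2)² = 61 × 3.24 = 198. The shortfall therefore does not depend on how d was standardised, provided both statements use the same scale.

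**5. Role of losses.** Analysed over allocated is 61/92, a loss of 31/92 = 34%. Losses alone do not explain the gap, since 92 with none would still give about 48%. At that loss rate, 199 analysed would mean 199 × 92/61 = 300.1, so 301 allocated.

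**6. Scope.** The 0.36 belongs to the pooled change. Group sizes are not in the text. Assuming an equal split, the detectable d between two groups is 2.802 × √(2/n per group): 0.88 for 61/3 per group, 0.81 for 71/3 and 0.72 for 92/3. For change within one group of 61/3 it is about 0.65 (paired t).

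**The case against.** The strongest reply is that the paragraph already gives the limit that matters. It calls 0.36 the minimal detectable size, the figure is correct, and a careful reader will see that smaller effects are not covered at 80%. That stands, and it lowers the severity.

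Second, 0.2–0.5 can be read as defining the weak-to-moderate band and not as a promise at every point in it. On that reading 0.36 lies within the band, as does 0.295 for all 92. The reading is fair, so it is too strong to say that the two statements flatly contradict each other. But the sentence then specifies no design: anything from 34 to 199 pairs would satisfy it. Either reading calls for the same edit.

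Third, 92 and 120 are recruitment counts, not a planned sample size. The full trial protocol is held by the ethics committee, and the original calculation is not in this document. A reader might infer that the trial was planned too small for d = 0.2. The document shows only that no count it reports reaches 80% there.

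Fourth, a reader might infer that a null global result will be taken as excluding weak effects. Nothing in the text says or plans this. The trial is called exploratory in section 1.1, and section 1.6 asks for independent validation of the regional findings. The risk is one of interpretation only.

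**Conclusion.** The design statement is not supported at its lower end. At d = 0.2 a pooled two-sided before-after test has about 34% power with the 61 analysed (about 32% by Wilcoxon) and about 48% with all 92. No reported count reaches 80% even one-sided, the maximum being 70% at 120. The achieved figure of 0.36 is sound as an approximation and needs only its test and comparison named; with the Wilcoxon test it is about 0.37.

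These results rest on the assumptions listed with the inputs, which are the ones that reproduce 0.36. They describe the imaging sample: the document does not say separately how many participants enter the clinical analyses, and with all 71 who finished, power at d = 0.2 would be about 38%. Severity is moderate to minor, because the wording misstates coverage of weak effects but the operative limit is in the same paragraph.

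**What to change.** Replace the 0.2–0.5 power statement in section 1.2 with the delivered figure, for example:

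> With 61 participants, the pooled two-sided before-after comparison (Wilcoxon test, alpha 0.05) has 80% power for d of about 0.36–0.37. Power at d = 0.2 is about one third, so a non-significant global result does not exclude weak effects. This figure does not apply to the three-group Kruskal-Wallis comparison.

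State how d is standardised. If the full protocol held a planned sample size and a single design effect, report them as the design target, separately from the achieved figure.

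The cost is a few sentences and a less favourable stated figure. No extra patients and no re-analysis are needed.

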1.3. Interventions

All groups underwent two months' ambulatory neuroproprioceptive PT led by well-educated (MSc.), experienced (at least two years' practice with pwMS) therapists specially trained in each method. Treatments were individually designed according to patient status. The therapists offered their full help and adopted the schedule, so each patient was able to complete the whole program. To increase adherence, therapists provided effective reminders and established confidential relationships.

Group 1 underwent 16 face-to-face sessions (1 hour, twice a week for two months) of MPAT (10), method developed and verified by our team. In this therapy, patients are corrected into a postural position where the joints are functionally centered. Afferent stimuli are then applied to activate motor programs in the brain, which then lead to the co-contraction of the patient's whole body when lying, sitting, standing up or moving forward. Activated programs are repeated under various conditions and in different situations and environments to teach the patients to automatically use the acquired motor skills in daily life. Therapy was realized at Faculty Hospital Royal Vineyard.

Group 2 underwent 16 face-to-face sessions (1 hour, twice a week for two months) of VRL (15), which is a standard approach for patients with MS in the Czech Republic. During the therapy, global patterns of the reflex locomotion are activated by stimulation of specific zones, with the individual placed in a precisely determined initial position (supine, prone and side laying, low kneeling position). These movement patterns have the qualities of the forward movement (locomotion) and the

movement responses are precisely defined. Reflex locomotion (reflex turning and reflex creeping) is used in therapy to activate involuntarily responses of muscle function, which are necessary for spontaneous movements. Therapy was realized at Motol University Hospital.

Group 3 underwent FES in PCP (16), a method developed at our workplace. Participants first underwent individual two-hour session consisting of postural correction using MPAT and the device (The WalkAide® System, Innovative Neurotronics Inc., [name]) programming. Patients received the device to be used use as much as they felt able to during their normal daily activities.. After fourteen days, the patients received the second individual two-hour session. The patients then continued to use the device daily for the next six weeks.

1.4. Clinical outcomes

Demographic and anamnestic data were collected by a neurologist, namely gender, age, length of disease, type of MS (relapsing-remitting, primary or secondary progressive) and EDSS.

The balance [Berg Balance Scale, BBS (17) and Timed up and go – TUG (18)] was examined and *patient-reported outcomes* [the 12-item Multiple Sclerosis Walking Scale, MSWS-12 (19) and MS impact with the 29-item Multiple Sclerosis Impact Scale, MSIS-29 (20)] were collected.

1.5. White matter integrity

All participants underwent magnetic resonance imaging on a 3T magnetic resonance scanner (Siemens Trio Tim, Erlangen, Germany) using a 12-channel phased-array head coil. The acquisition protocol consisted of T1-weighted and T2-weighted

anatomical scans, and diffusion weighted imaging using spin echo epi sequence with following parameters TR=9100 ms, TE=96 ms, FOV=260x211 mm, 64 contiguous axial slices with 2 mm thickness, b=0 and 1100 s/mm², 64 gradient directions.

For the DTI pre-processing, a combination of FSL tools (FMRIB Software Library, <http://www.fmrib.ox.ac.uk/fslwiki>, version 5.0) and MRtrix3 was used. The data was initially de-noised and corrected by applying the MRtrix dwidenoise function (21) and Gibbs ringing correction (22). The resulting images were visually controlled, and the volumes with low quality were discarded. The 'Eddy current correction' was subsequently applied (23).

In the context of neuroproprioceptive PT, we did not expect changes in a particular area; hence we analyzed FA across the white matter using a global changes of FA as well as FA changes in 48 white matter regions.

FA global change and changes in 48 regions of interest

A diffusion tensor was fitted to each voxel of the brain, and a fractional anisotropy (FA) map was created for each subject (24). The images were further analyzed using tract-based spatial statistics (TBSS) (25). The TBSS routine consisted of three steps: 1) non-linear registration of all FA images to a chosen template – we chose the FMRIB58_FA standard-space image as a target; 2) application of the non-linear registration identified in the first step, affine registration of each subject to MNI152 space and skeletonization of the mean image; 3) thresholding of the mean skeleton (we used 0.3 as a threshold) and a projection of individual subjects FA maps onto the mean skeleton. Primarily, the (global) mean of the projected FA values over the whole skeleton were compared among subjects.

The resulting skeletonized images were parcellated using the ICBM-DTI-81 white- (26) matter labels atlas consisting of 48 regions, and the mean FA value for each region was computed (regions are listed in Table 3).

1.6. Statistical analysis

The resulting dataset was further analyzed using the non-parametric Wilcoxon test for assessing the difference between visits. Differences between the treatment groups were identified using the Kruskal-Wallis test. All statistical analyses were performed using Matlab (MATLAB version R2018b). Note that the region-wise analysis was considered exploratory so that there was used an uncorrected significance threshold of 0.05 to select the strongest effects for description. Due to the multiple undertaken tests, many of the presented localized effect results can constitute false positive findings, and thus the observed effects serve rather as initial findings calling for independent validation in a follow-up study. The conservative Bonferroni-corrected threshold across 48 regions would correspond to $0.05/48 \approx 0.0001$, which was not reached by any single one of the effects. However, this is to be expected, as the study sample size was not designed for confirmatory testing of such a large set of hypotheses, but rather for global effect testing. This additional exploratory analysis is intended to provide the reader with further information on the presence/absence and spatial distribution of any potential localized effects outside the global hypotheses testing.

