1.1. Study design

The Multi-Arm Parallel-Group Exploratory Trial (NCT04355663) was realized between May 2015 and May 2017. MS patients were divided into three groups by an independent study coordinator according to availability of each therapist (in Groups 1 and 2) and amount of FES devices to borrow (in Group 3), and underwent three kinds of PT. At baseline and after the end of the two months' therapeutic program, white matter integrity was estimated from DTI and a blinded assessor evaluated clinical outcomes.

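### The d=0.36 power figure fits only a pooled before-after test, and with three active arms and no time control that test shows change over two months, not an effect of physiotherapy.

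*Combined protocol and SAP*

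**What the plan says.** Section 1.1 describes patients who "underwent three kinds of PT", with DTI and clinical outcomes measured at baseline and after the two-month programme. Allocation followed therapist availability and the number of devices that could be lent. Section 1.3 describes the three programmes (MPAT, VRL, and FES in PCP), all of them active. No untreated, waiting-list or sham group, rescanned healthy group or repeated pre-treatment baseline is described.

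Section 1.6 gives two tests: the "non-parametric Wilcoxon test for assessing the difference between visits", and a Kruskal-Wallis test for differences between groups. It says the sample size "was not designed for confirmatory testing of such a large set of hypotheses, but rather for global effect testing".

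On power, Section 1.2 states that "The study was powered in order to provide 80% power for weak to moderate effect size". After exclusions "resulting in 61 participants entering the central analysis", it gives 80% power at p<0.05 for a minimal d of 0.36. It does not say which test this refers to. Section 1.5 says skeleton-mean FA was compared across subjects, which does not settle the matter.

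The caution in Section 1.6 about false positives concerns multiplicity over the 48 regions. Nothing comparable is said about interpreting the global test.

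**The concern.** The null hypothesis of a before-after test is no change between visits. It equals no effect of therapy only if nothing else moves the outcome over two months. Candidate causes differ by outcome: scanner drift and disease course for FA; disease course, practice and expectation for the clinical measures. With no group observed over the same interval without therapy, the test cannot separate these from a therapy effect.

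This matters because the plan's power statement appears to belong to this test, and the plan speaks of effects without saying effects of what. A significant global FA change could then be read as evidence that physiotherapy alters white matter. The between-group test might seem to supply the missing control, but it contrasts one active programme with another.

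**Working it through.** **Inputs.** From Section 1.2: n=61 analysed, 80% power, p<0.05, d=0.36. From Sections 1.1 and 1.3: three arms, all active. Assumed: a two-sided test; arms of about 61/3 = 20.33, since the text does not give arm sizes among the 61; and effects in units of the SD of within-patient change.

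**Step 1. Reproduce d=0.36.** With z(0.975)+z(0.80) = 1.960+0.842 = 2.802:

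- Pooled before-after, normal formula: 2.802/√61 = 0.359. In reverse, (2.802/0.36)² = 60.6, which rounds up to 61. Power at d=0.36 is 80.3%.
- Pooled before-after, paired t: 0.365, with power 79.0% at d=0.36.
- Pooled before-after, Wilcoxon at efficiency 3/π: 0.373, with power 77.1% at d=0.36. This is close, but less exact than the normal formula.
- Pooled before-after, one-sided: 0.318 to 0.322. No match.
- Pooled before-after with 71 or 92 patients (paired t): 0.337 or 0.295. No match.
- Before-after within one arm: 2.802/√20.33 = 0.62. No match.
- Two groups of 30.5: 2.802×√(2/30.5) = 0.72. No match.
- Two arms of 20.33: 2.802×√(2/20.33) = 0.88 (0.90 by t). No match.
- Three-group ANOVA: f = 0.41, or one arm differing from the other two by about 0.87 SD. No match.

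Of these readings, only the two-sided before-after comparison pooling all 61 gives the stated figure.

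**Step 2. What that test does under a shift that is not therapy.** Suppose therapy has no effect and every patient's outcome moves by δ SD of change. The rejection rate is then the power of the paired test at δ (non-central t, 60 degrees of freedom, non-centrality δ√61). The Wilcoxon and Kruskal-Wallis rates come from 4,000 simulated trials with normal changes and arms of 20, 20 and 21.

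| Assumed δ | Paired t | Wilcoxon (simulated) | Kruskal-Wallis (simulated) |
|---|---|---|---|
| 0.1 | 12% | 12% | 5% |
| 0.2 | 34% | 32% | 5% |
| 0.3 | 64% | not run | not run |

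The Kruskal-Wallis rate stays at its nominal level because a common shift cancels between arms. A benefit common to all three programmes cancels in the same way.

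**Step 3. What the arm contrasts can show.** With about 20 per arm, a pairwise contrast has about 20–21% power at d=0.36. The three-group test has about 19% power when one arm differs by 0.36 SD. The unadjusted 95% CI half-width for a pairwise difference is about 1.96×√(2/20.33) = 0.61 SD of change. A two-arm contrast with 80% power at d=0.36 would need 122 per arm, 244 in all.

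**The case against.** The best defence is that the plan makes no causal claim. Section 1.6 presents the Wilcoxon test as assessing a difference between visits, Section 1.1 calls the trial exploratory, and no sentence in the supplied text attributes a change to therapy. This stands. A reader might infer that the plan already credits physiotherapy with any change, but the documents do not say so. What is missing is an explicit limit.

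Second, the design has safeguards. Entry required three months of stable status and treatment, one scanner was used, and the assessor was blinded. These reduce the risk without removing it. Blinding does not deal with practice on BBS and TUG, or with expectation in the patient-reported MSWS-12 and MSIS-29. Not every mechanism fits every outcome: practice does not apply to FA, and regression to the mean is a weak explanation for FA because entry does not select on it. Large steady scanner drift is also hard to credit. If enrolment was spread over a study that "was realized between May 2015 and May 2017", 0.3 SD per two months would accumulate to 12×0.3 = 3.6 SD over 24 months.

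Third, the percentages in the table are a power curve under assumed shifts and would hold for any paired test with n=61. A reader might take them as the trial's false-positive rates. They are not, since nothing in the documents indicates that a shift of any such size occurred.

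Fourth, a between-group test is planned, so it would be wrong to say the trial has no comparison of arms. But that test compares active programmes allocated by availability, with Groups 1 and 2 treated at different hospitals. It cannot answer whether physiotherapy as such changes the outcome.

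**Conclusion.** The point holds as a limit on interpretation. The power figure in Section 1.2 is matched only by the pooled before-after comparison. This is an inference from arithmetic, because no test is named. That comparison describes change over two months and cannot attribute it to therapy, and the Kruskal-Wallis test does not fill the gap.

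The power figure belongs to the 61 patients with usable DTI and, read with Section 1.6, to global FA. It should not be extended to the clinical outcomes, although the attribution limit applies equally to them. The size of any non-therapy shift is unknown. The 12%, 34% and 64% rates show how readily the test would respond to an assumed one, and do not show that bias is present. The imprecision of the arm contrasts rests on the assumed equal split.

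A reader might also conclude that reanalysis can supply the missing control, or that a control arm must be added. Neither follows: no analysis of these data creates a time control, and the study is complete. What can be corrected is what the tests are said to show.

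**What to change.** In Section 1.6:

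1. Name the test to which d=0.36 refers, whether it pools the three arms, and that it concerns global FA in the 61 with usable DTI. State that the visit test, for FA and for the clinical outcomes, describes change over time and supports no claim that therapy caused it.
2. Report between-arm differences in change, adjusted for the baseline value, with 95% CIs, in addition to or in place of the Kruskal-Wallis p-value. Label them non-randomised, and say that they cannot show a benefit common to all arms.

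Optional: if scan dates were kept and enrolment was staggered (neither is stated), fit a sensitivity model for global FA with visit and calendar scan date. Describe it as a check on smooth scanner drift only; disease course stays tied to visit.

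The cost is wording and a small amount of modelling on existing data. The downside is that the before-after result becomes descriptive, while the arm contrasts are imprecise, with a detectable d of about 0.88 at 80% power under the assumed split of about 20 per arm.

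### The only between-arm analysis is a three-group Kruskal-Wallis test, which names no group, direction or size; gated pairwise comparisons with descriptive estimates would fill the gap, at low precision and without causal attribution.

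*Combined protocol and SAP*

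**What the plan says.** Section 1.6 describes two tests. Change over time is examined "using the non-parametric Wilcoxon test for assessing the difference between visits". For the arms, the whole text is: "Differences between the treatment groups were identified using the Kruskal-Wallis test". No reference arm, pairwise contrast, estimate of a difference between arms or confidence interval is described. The section also does not say whether the Wilcoxon test is run within each arm or on all participants together, or which quantity enters the Kruskal-Wallis test. I take that quantity to be the change from baseline.

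Section 1.3 describes VRL (Group 2) as a therapy "which is a standard approach for patients with MS in the Czech Republic", and presents MPAT and FES in PCP as methods from the team's own workplace. No section names VRL as the control.

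On numbers, section 1.2 says "92 were allocated into three groups; from these 71 participants finished their therapeutic programs", with low-quality DTI exclusions "resulting in 61 participants entering the central analysis". It gives 80% power at p<0.05 for d=0.36 with this sample, without saying for which comparison. Section 1.5 sets the main imaging measure: "Primarily, the (global) mean of the projected FA values over the whole skeleton were compared among subjects".

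**The concern.** A significant Kruskal-Wallis result on three groups rejects only the hypothesis that all three share one distribution. Section 1.6 says the test identifies differences between treatments, which is more than it can do. If the plan is followed as written, a significant result stops there: the reader does not learn whether MPAT, VRL or FES in PCP stands apart, whether it did better or worse, or by how much. A non-significant result is no more informative, because without an estimate and interval nobody can tell similar groups from imprecise data.

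The question most readers will bring is whether either in-house method differs from the approach described as standard. No analysis in the plan addresses it. The follow-up study that section 1.6 calls for would also need pairwise estimates of the difference in change, and the plan does not produce them.

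**Working it through.** **1. Inputs.** Total analysed 61, alpha 0.05, power 80%, d=0.36 and planned range d=0.2-0.5 (section 1.2); three arms (sections 1.1 and 1.3). Per-arm numbers are in a figure that is not available, so I assume 20/20/21 (MPAT/VRL/FES), with 25/21/15, 15/21/25 and 28/18/15 as the range. Simulations use normal change scores, 40,000 trials per scenario.

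**2. The plan's own figure.** For a two-sided paired comparison on all 61:

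d = (1.960 + 0.842)/√61 = 2.802/7.810 = 0.359.

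The noncentral t version gives 0.365. So d=0.36 reproduces as a pooled before-after figure. The other readings tried do not give it: one-sided paired 0.318; 61 split into two groups, 2.802 × √(2/30.5) = 0.72; three-group F test f=0.41, which is d of about 0.87 when one arm differs. At d=0.36 in one arm, the three-group F test has about 19% power.

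**3. Why gating works within one endpoint.** Call the pairwise nulls (equal distributions) A=B, B=C and A=C. If any two are true, so is the third, so every intersection of two or more is the global null. Kruskal-Wallis already tests that at 0.05. By closure, once it rejects, each pair can be tested at the full 0.05.

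Simulated checks:
- Global null, all three gated contrasts: family-wise error 0.048 (0.046-0.048 across arm splits).
- MPAT far from the other two: false-positive rate for FES v VRL 0.049 (0.045-0.049).
- Global null, all three contrasts without the gate: 0.120.

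In the null runs every Kruskal-Wallis rejection came with at least one significant pair, so an ungated pair is significant while the omnibus test is not in 0.120 − 0.048 = 0.072, about 7% of trials. Unadjusted 95% intervals shown for every pair would conflict with the gate at about that rate.

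**4. Across endpoints.** Closure does not help here. Global FA and the four clinical measures make five endpoints. If they were independent, the chance of at least one false omnibus rejection would be 1 − 0.95⁵ = 1 − 0.774 = 0.226.

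**5. Power when MPAT alone differs.**

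| d | Kruskal-Wallis rejects (20/20/21) | Gated MPAT v VRL declared (20/20/21) | Gated contrast, other splits |
|---|---|---|---|
| 0.36 | 18% | 12% | 11-14% |
| 0.5 | 32% | 24% | 21-27% |
| 0.9 | 81% | 72% | 64-78% |

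**6. Detectable pairwise effect, ignoring the gate.** For 20 v 20: 2.802 × √(1/20 + 1/20) = 0.89 (noncentral t 0.91). The range is about 0.8 for 25 v 25 to 1.06 for 15 v 15. If clinical outcomes used all 71 completers, 71/3 ≈ 23.7 per arm gives 2.802 × √(2/23.7) = 0.81. The number per arm for 80% power is 2 × (2.802/d)²: 122 at d=0.36 and 63 at d=0.5.

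**The case against.** The strongest reply is that this is an exploratory study, already completed, whose sample was meant for global effects. At the effects section 1.2 has in mind, the omnibus test would reject in only 18-32% of trials, so the pairwise step would seldom be reached. Adding it now is post hoc. That stands, and it limits the point to what is reported and how it is described. It does not remove the point: the false-positive caveat in section 1.6 is written for the 48-region analysis, and pairwise estimates with intervals are informative whether or not the gate opens.

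Four stronger readings are tempting, and the documents do not support them.

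- *The contrasts would show whether MPAT or FES in PCP works differently from VRL.* Section 1.1 says groups were formed by therapist availability and the number of devices, and section 1.3 places MPAT and VRL at different hospitals. A contrast cannot separate therapy from site, therapist or allocation. The existing Kruskal-Wallis test has the same limit.
- *Power is ample.* Figures of 72-81% arise only at d=0.9, well above the planned 0.2-0.5.
- *VRL is the control.* It is called a standard approach and never designated as the reference, so all three pairs should be compared.
- *The plan infers arm differences from within-arm before-after p-values.* Section 1.6 does not say the Wilcoxon test is run by arm, and d=0.36 matches a pooled test.

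**Conclusion.** The gap is real and worth closing: the plan has no between-arm analysis that yields a group, a direction or a size. Gated pairwise tests supply the first two at no alpha cost within a single endpoint, and Hodges-Lehmann estimates supply the size. The gain is modest. With about 20 per arm, a pairwise contrast reaches 80% power only near d=0.9, so a non-significant contrast would say little, and a significant one would locate a group without explaining why it differs.

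The power figures rest on the assumed arm sizes and normal change scores; the ranges above show how far the split matters. The closure argument depends on neither, but it needs exactly three groups and covers one endpoint at a time. A reader might infer that the contrasts turn this into a confirmatory comparison with standard care. Non-random allocation, the undeclared reference and the post hoc timing all rule that out.

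**What to change.** Add to section 1.6:

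> For change in global FA and in each clinical outcome (BBS, TUG, MSWS-12, MSIS-29), but not for the 48 regions, if the Kruskal-Wallis test is significant at 0.05, all three pairs of groups are compared by Wilcoxon rank-sum test, each at 0.05. With three groups this controls family-wise error within that endpoint only, not across endpoints. Hodges-Lehmann differences in change with 95% confidence intervals are reported for every pair as descriptive, unadjusted estimates; no significance is claimed for any pair when the Kruskal-Wallis test is not significant. These contrasts are exploratory and post hoc. Because allocation was not random and the therapies were delivered at different hospitals, a difference between groups cannot be attributed to the therapy.

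In section 1.2, state which comparison d=0.36 refers to (it matches the pooled before-after change on all 61) and give the between-arm detectable effect from the actual arm sizes, about d=0.9 if they are near 20. In section 1.6, state whether the Wilcoxon test is pooled or by arm, and which quantity enters the Kruskal-Wallis test.

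The cost is a few lines of text and code, with no new data. The downside is wide intervals that show openly how little the between-arm data can say.
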